After obtaining consent and ensuring all inclusion and exclusion criteria are met, randomization will be done in the emergency room prior to treatment using a web-based dynamic randomization system. Our randomization algorithm will be accessible to the study investigators and staff through a separate web page accessible only through the REDCAP database module. Covariate adaptive randomization will be used to balance the distribution of age (<60, 60-69, 70-79, 80-85 years old), presentation NIHSS (6-9, 10-15, 16-20, >20), center, clot location (M1, ICA), treatment time window (0-8, 9-16, 17-24 hours from onset to randomization time), CTP/MRP core volume (<50cc, 50-100cc, >100cc), presence or absence of target mismatch profile (mismatch ratio ≥ 1.8 & mismatch volume ≥ 15 cc) and hemisphere (right, left) between the two treatment groups.

The randomization algorithm we are going to implement is the algorithm developed by Pocock and Simon (1975)²⁷, i.e., minimization method. Through this algorithm, the assignment of a new patient to a treatment group is determined so as to minimize the differences between the groups in terms of these important key baseline variables. Unlike traditional stratified randomization, the minimization method works toward minimizing the total imbalance for all factors together instead of considering mutually exclusive subgroups, that is, we will not be creating these mutually exclusive subgroups during the randomization. Therefore, this approach is not restricted by the number of variables and the possible combinations of levels of balancing factors. Further details about Randomization can be found in Appendix A.

Eligible patients will be randomized into thrombectomy plus medical management vs medical management alone at a 1:1 ratio. The minimization algorithm is intended to balance the baseline characteristics between the two study arms, thrombectomy vs. medical management. The algorithm is not intended at the level of imaging profile subgroup. When a new patient is enrolled, the site will enter the stratification factor values into the dynamic randomization webpage and the treatment assignment will be determined immediately. An emergency 1-800 number will be provided if web-based randomization is not available due to exigent circumstances.

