Considering a prior assumption that the EVT effect is largest in the patients with good imaging profile and treated within the shortest time window, we assume that the highest effect of EVT will be observed in G1A. Then the effects get decreased gradually in G1B, G2A, G2B, G3A, and the lowest effect will be observed in G3B. According to this adaptive design, when a most promising subgroup needs to be selected at the time of interim (or final) analysis, we will compare the GLR statistic among five cumulative groups, that is, G1A, G1A+G1B (i.e., Group 1), G1A+G1B+G2A, G1A+G1B+G2A+G2B (i.e., Group 1+Group 2), and G1A+G1B+G2A+G2B+G3A.

Primary analysis: The primary endpoint is the distribution of scores on the modified Rankin Scale (mRS) at day 90. The null hypothesis will be tested at the interim and final analysis using a normal approximation of the Wilcoxon-Mann-Whitney test (the GLR test). The principle of the intention to treat will be applied for the primary analysis. An additional analysis of the primary endpoint will be the same rank-based analysis comparing the 90-day mRs distribution between treatment groups while stratifying for prognostically important covariates. We will use the Generalized Cochran-Mantel-Haenszel test (CMH) to evaluate whether there is a uniform shift on the mRS distribution from one group to the other after stratification. The CMH test will be stratified by these variables used in the covariate adaptive randomization. For age, NIHSS, treatment time window, and CTP core volume, we will consider them as continuous variables in this adjusted analysis.

Power and sample size considerations Based on prior reported data, the following distributions were projected on the mRS at 90 days in EVT and MM groups for SELECT 2 in the overall population.

	mRS at day 90							Total
	0	1	2	3	4	5	6	
Endovascular group	4%	8%	12%	16%	19%	13%	28%	100%
Medical group	1%	4%	9%	14%	19%	10%	43%	100%

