This distribution corresponds to a standardized effect of 0.34 for the primary analysis. Based on these data, the fixed sample size for a non-adaptive design requires a total of 376 patients (188/arm) to have 90% power at an alpha of 5% (Wilcoxon-Mann-Whitney test); We add additional 184 patients for the adaptive design to reach a maximum sample size of 560. We will conduct two interim analyses when we reach the number of patients at 200 and 380. Through extensive simulation studies, we have shown that with 560 patients in total for the adaptive design, we will have around 91% power to test for a standardized effect size of 0.34 in the overall population (assuming homogeneous EVT effect across six disjoint groups) by controlling an overall (one-sided) Type I error rate at 2.5%.

Efficacy and futility bound At each analysis (two interim analyses and the final analysis), an efficacy bound will be set to decide if the study should be stopped for efficacy while controlling the overall (one-sided) Type I error rate at 2.5%. At each interim analysis, a futility bound will be set to decide if the study should continue recruitment in the overall group, shift accrual and testing to a subgroup, or stop the trial entirely. When the futility bound is crossed and the optimal subgroup is selected, the maximum analyzed sample size will not be fixed but a random variable (smaller than the fixed maximum sample size 560). Due to the reduction in the maximum number of patients available for analysis at the end of the study, our design allows

an easier futility stop after subgroup selection. Further details regarding efficacy and futility bounds at interim and final analyses is provided in Appendix B.

First interim analysis (n=200 randomized and completed 90-day follow-up): The null hypothesis is tested in the entire patient cohort:

1. If neither efficacy nor futility bound is crossed, the trial continues enrollment to the 2nd interim analysis.
2. If the efficacy bound is crossed, the trial stops and efficacy is declared in the overall cohort.
3. If the futility bound is crossed, the optimal subgroup is selected based on the GLR statistic and the null hypothesis is tested in this selected subgroup:
 - 3.1. If neither bound is crossed, the trial will continue with enrollment limited to the selected subgroup
 - 3.2. If the efficacy bound is crossed, the trial stops and efficacy is declared in the selected subgroup

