 - 3.3. If the futility bound is crossed, the trial stops for futility.

Note: the futility bound is relaxed as described above, based on the expected maximum number of patients in the trial at completion (i.e. 560 minus the number of patients already enrolled in the groups that will no longer be open for enrollment).

Second interim analysis (n=380 randomized and completed 90 day follow-up): After the first interim analysis, the trial proceeds to this stage under two scenarios: (1) continuing enrollment in the overall population (i.e., option 1 above) and (2) limiting enrollment to a selected subgroup (i.e., option 3.1 above). When scenario (1) happens, the testing at the 2nd interim analysis is identical to the first interim analysis. When scenario (2) happens, the null hypothesis is tested in that selected subgroup:

1. If neither bound is crossed, the trial continues to the final analysis with an enrollment of $560-380=180$ additional patients limited to the selected subgroup

2. If the efficacy bound is crossed, the trial stops and efficacy is declared in the selected subgroup
3. If the futility bound is crossed, the trial stops for futility.

Final analysis (n=560 randomized and completed 90-day follow-up): After the 2nd interim analysis, the trial proceeds to the final stage under two scenarios: (1) continuing enrollment in the overall population and (2) limiting enrollment to a selected subgroup.

When scenario (1) happens, the null is tested in the overall population:

1. If the efficacy bound is crossed, EVT is declared efficacious in the overall population.
2. If the efficacy bound is not crossed, the optimal subgroup is selected and the null is tested in that group:
 - 2.1. If the efficacy bound is crossed, EVT is declared efficacious in that subgroup
 - 2.2. If the efficacy bound is not crossed, EVT will be declared of no benefit.

When scenario (2) happens, that is, limiting enrollment to a subgroup (either selected at the 1st or 2nd interim analyses), the null hypothesis is tested in that selected subgroup only. Efficacy or lack thereof will be declared as per options 2.1 and 2.2 above.

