Appendix B. Efficacy and futility bounds for interim and final analysis

At the l th interim analysis, let W_i^l be the sum of the ranks of Rankin scores from the endovascular group in the patient subgroup Π_i , $j = 1, \dots, J$. In our trial, we defined $J = 6$ groups with Π_j denotes the entire patient population and Π_1, \dots, Π_5 denote the subgroups of G1A, G1A+G1B, G1A+G1B +G2A, G1A+G1B +G2A +G2B, G1A+G1B +G2A +G2B +G3A, respectively.

The standardized Wilcoxon statistic for patient subgroup Π_i is

$$Z_i^l = \left\{ W_i^l - \frac{n_i^l(n_i^l + n_{0i}^l + 1)}{2} \right\} / \left\{ \frac{n_i^l n_{0i}^l (n_i^l + n_{0i}^l + 1)}{12} \right\}^{1/2},$$

where, n_i^l and n_{0i}^l denote the numbers of patients enrolled into the endovascular group and medical management group at the l th interim analysis, respectively.

At the l th interim analysis, we will terminate the trial and claims efficacy for the endovascular group if the following efficacy bound is crossed, that is,

$$Z_j^l \geq b.$$

Otherwise, we will proceed to the subgroup selection if the following futility bound is crossed, that is,

$$\widetilde{Z}_j^l \leq \widetilde{b},$$

where

$$\widetilde{Z}_j^l = \left\{ W_i^l - \frac{n_i^l(n_i^l + n_{0i}^l + 1)}{2} - n_i^l n_{0i}^l \theta \right\} / \left\{ \frac{n_i^l n_{0i}^l (n_i^l + n_{0i}^l + 1)}{12} \right\}^{1/2}.$$

When the above criteria is satisfied, a subgroup \hat{I} with the largest value of Z_i^l for $i \neq J$ is chosen. The future enrollment of the trial will include patients of this subgroup only, while the maximum total sample size is still $N=560$.

Similar to testing the efficacy and futility in the entire population, at stage l' , we will terminate the trial and claim efficacy for the endovascular group in this selected subgroup if the following efficacy bound is crossed

$$Z_j^{l'} \geq b.$$

We may also terminate for futility if

$$\widetilde{Z}_j^{l'} \leq \widetilde{b}.$$

If neither the efficacy nor futility bound for the entire population ever occurs, the trial proceeds to the final stage and we terminate the trial and claim efficacy for the endovascular group if

$$Z_j^{l=3} \geq c.$$

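### The interim rule has no harm bound on the primary mRS endpoint, so a trial that shows overall harm can go on enrolling in a subgroup that itself favors medical management

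*Combined protocol and SAP*

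**What the plan says.** Section 6.1 gives three outcomes at the first interim analysis: continue, stop for efficacy, or cross the futility bound. In the third case, "If the futility bound is crossed, the optimal subgroup is selected based on the GLR statistic", and the null hypothesis is tested in that subgroup. Enrollment continues in the subgroup if neither bound is crossed (step 3.1). The trial stops for efficacy under 3.2 and for futility under 3.3. If the whole population is still being enrolled at n=380, the same steps apply.

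Section 6.1 adds that "the futility bound is relaxed as described above, based on the expected maximum number of patients in the trial at completion", meaning 560 minus those already enrolled in closed groups. Appendix B confirms the restriction ("The future enrollment of the trial will include patients of this subgroup only") and gives b = 2.604, futility bound -1.897, c = 2.772 and θ = 0.0791. It prints one θ, calculated at N = 560, and no recalculated value for a subgroup.

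Section 10 sets separate two-step Bayesian rules for sICH and 90-day mortality in endovascular patients. They are guides only, and the DSMB decides independently. Section 9 tells the reader that the adaptive design will remove subgroups that respond unfavorably.

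**The concern.** Futility and harm are different findings, but the rule gives them one label and one action. A result favoring medical management at Z = -3 is handled like Z = 0: the best-looking of five cumulative subgroups is chosen and tested. Step 3.1 has no condition on the sign of the subgroup estimate. The futility bound is set against the projected benefit, so in a small subgroup it is crossed only when Z is well below zero.

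Patients could therefore go on being randomized to an invasive procedure when the trial as a whole shows nominally significant harm and the selected subgroup also leans the wrong way. Table 3 does not show how the design behaves in that case. Its lowest cell effect is -0.1, and no row has a negative average effect.

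**Working it through.** Positive Z is taken to favor thrombectomy, as Section 6.1 intends.

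**1. The plan's own figures.** θ = (1.960 + 1.2816)/√(3 × 560) = 3.2415/40.99 = 0.0791, as Appendix B states. For the fixed design, the projected mRS table gives P(thrombectomy better) + ½P(tie) = 0.59375. The tie-corrected Noether formula gives N = 0.9421 × 3.2415² / (3 × 0.09375²) = 375.4, which rounds to the stated 376. So the constants are read correctly.

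**2. Futility on the ordinary Z scale.** With 1:1 allocation, the shifted statistic is Z - θ√(3n). Crossing -1.897 means Z ≤ 3.2415 × √(n/Nmax) - 1.897.
- Overall, n=200: 3.2415 × √(200/560) - 1.897 = 1.937 - 1.897 = 0.04.
- Overall, n=380: 2.670 - 1.897 = 0.77.

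**3. Subgroup cut-offs at n=200**, with sizes expected from the mix assumed for Table 3 (14/6/14/6/42/18%). The relaxed Nmax is 560 minus patients in closed groups.

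| Selected subgroup | n | Fixed (Nmax 560): stop at Z ≤ | Relaxed Nmax | Relaxed: stop at Z ≤ |
|---|---|---|---|---|
| G1A | 28 | -1.17 | 388 | -1.03 |
| G1 | 40 | -1.03 | 400 | -0.87 |
| G1+G2A | 68 | -0.77 | 428 | -0.60 |
| G1+G2 | 80 | -0.67 | 440 | -0.51 |
| All but G3B | 164 | -0.14 | 524 | -0.08 |

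Any Z between the cut-off and 0 favors medical management and leaves the subgroup open.

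**4. How often.** Assume a uniform standardized effect of -0.34, the mirror image of the planning value ("This distribution corresponds to a standardized effect of 0.34 for the primary analysis"), and the Wilcoxon efficiency factor √(3/π) = 0.977. Mean overall Z at n=200 is -0.34 × (√200/2) × 0.977 = -2.35, so P(Z ≤ -1.96) = Φ(0.39), about 65%. Normal-approximation simulation of the first interim, choosing the subgroup with the largest Z, gives:

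| | Fixed | Relaxed |
|---|---|---|
| Enrollment continues, all trials | 65% | 60% |
| Selected subgroup's Z negative, among those continuing | 61% | 57% |
| Continues, given overall Z ≤ -1.96 and selected Z ≤ 0 | 49% | 41% |

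At a uniform effect of -0.30 the last row is 51% and 43%.

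**5. Does this reconstruction match the plan?** Partly. With the relaxed bound, type I error is 2.1% (Table 3: 2.0%). Power is 87.7% at 0.32 (86.0%), 83.0% at 0.30 (81.1%), 79.7% in scenario #4 (78.5%) and 62.8% in #7 (60.5%). The null row does not match: 46% futility stops and 458 patients, against 59.1% and 426.

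A stricter reading sets the subgroup maximum at 560 times its share. For G1A that is 78.4, and 28/78.4 = 200/560, so the cut-off becomes 0.04. The same holds for every subgroup at its expected size. That reading gives 67% and 395 under the null, so the two readings bracket the stated values. Under it, continuation with a negative subgroup after overall Z ≤ -1.96 falls to 0% at expected group sizes and about 2% when sizes vary.

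**6. Section 10 as a backstop.** With mirror-image mortality (43% thrombectomy, 28% medical) and 50 per arm in the ≤100cc stratum, step 1 (26 or more deaths) is met in 13% of trials, and both steps in 6-7%. With 22 medical deaths among 50, step 2 needs 36 endovascular deaths: 72% - 44% = a 28-point excess.

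**The case against.** A reader might infer that the rule has no exit at all when thrombectomy is harmful. The documents do not support that. Section 6.1 lists stopping the trial entirely among the interim outcomes, and step 3.3 does so. At a uniform -0.34 it fires at the first interim in about 34-40% of trials. At -0.30, with the relaxed bound, about 99% of simulated trials end in a futility stop.

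A reader might also infer that a trial with significant overall harm and a negative selected subgroup normally continues. That is too strong: it is about even under the fixed bound, and most such trials stop under the relaxed bound.

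Three further points carry weight. The percentages rest on a reading of the subgroup maximum that does not reproduce Table 3's null row, and under a stricter reading the problem almost disappears. Uniform harm of -0.34 is an assumption, not a projection in the plan. Oversight is broader than one mortality look: Section 10 has further strata and an sICH rule, the DSMB reviews semi-annually and decides independently, and there is a medical safety monitor. The DSMB charter is an attachment not among the documents reviewed, and it may contain harm guidance.

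None of this supplies a harm bound on mRS. The stricter reading is not the text: Section 6.1 defines the maximum as 560 minus patients in closed groups. It also fits the stated power less well in scenario #7 (55.4%, against 60.5% stated and 62.8% for the written rule). If the code differs from the text, the rule actually used needs to be written down.

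**Conclusion.** The point holds in a limited form. The interim rule has no harm bound on the primary endpoint, and a selected subgroup may continue with a negative Z: between about -1.17 and 0 for G1A (-1.03 if relaxed), and over a narrower range for larger subgroups. These cut-offs follow by arithmetic from Section 6.1 and Appendix B at the expected group sizes.

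The frequency is less certain. Given overall Z ≤ -1.96 and a non-positive selected subgroup, it is about 49% (fixed) or 41% (relaxed, as written) at an assumed uniform -0.34, and perhaps 0-2% if the code uses a smaller subgroup maximum. The Section 10 rules cover only sICH and mortality, so they do not replace a harm rule on mRS, although the DSMB keeps full discretion. This is a cheap improvement to the design and does not invalidate it.

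**What to change.** In the interim steps of Section 6.1 and in Appendix B, add a guideline for the DSMB: if overall Z ≤ -1.96 at an interim analysis and the selected subgroup's Z is ≤ 0, the trial stops rather than continuing in that subgroup. State the subgroup futility maximum actually used in the simulations. Re-run Table 3 and add uniform-harm rows over a range of effects, for example -0.1 to -0.34.

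The gain at a uniform -0.34: continuation after the first interim falls from 65% to 39% (relaxed: 60% to 37%), and average N from 320 to about 272 (relaxed: 309 to 268).

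The cost is one decision line and a simulation re-run. Power changes by 0.3 points or less in scenarios #3, #4, #6 and #7. With Groups 1-2 at +0.4 and Group 3 at -0.3 it falls by 0.3 to 0.5 points. Type I error stays at about 2%. Because the guideline needs both conditions, it leaves enrichment open when the selected subgroup looks favorable. Other triggers are possible: stopping on overall Z ≤ -1.96 alone, or requiring a positive subgroup Z to continue, costs up to 1.8 points of power in scenario #7 (62.8% to 61.0% for the latter).

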Operating characteristics of the adaptive design: We have conducted simulations (5000 simulated trials) to evaluate the performance of the adaptive design (max n=560) and compare it to a traditional fixed sample-size design (fixed n=560) under various scenarios (see **Table 3**, below). For the simulations the effect size is expressed as a standardized effect with normal approximation, where a standardized effect of 0.32 or 0.30 corresponds to a conservative projected effect of EVT (anticipated effect 0.34; see section of Power and sample size considerations). We assume that we will observe the number of patients in G1A, G1B, G2A, G2B, G3A, G3B with 14%, 6%, 14%, 6%, 42%, and 18%, respectively.

Scenario	Standardized effect in groups G1A, G1B, G2A, G2B, G3A, G3B							Average standar d. effect	Adaptive Design		Fixed Design	
									Average No. randomized	Power	Number randomized	Power
#0	0	0	0	0	0	0	0	0	426	2.0%	560	2.5%
#1	0.32	0.32	0.32	0.32	0.32	0.32	0.32	0.32	376	86.0%	560	95.8%
#2	0.3	0.3	0.3	0.3	0.3	0.3	0.3	0.3	393	81.1%	560	93.3%
#3	0.4	0.4	0.4	0.4	0	0	0.16	0.16	500	74.1%	560	45.7%
#4	0.4	0.4	0.4	0.4	-0.1	-0.1	0.1	0.1	502	78.5%	560	21.2%
#5	0.4	0.4	0.3	0.3	0	-0.1	0.122	0.122	513	67.1%	560	29.2%
#6	0.5	0.5	0	0	0	0	0.1	0.1	503	70.6%	560	21.2%
#7	0.5	0	0	0	0	0	0.07	0.07	503	60.5%	560	12.8%

Table 3. Under the null (Scenario #0), the adaptive design controls the total Type 1 error below 2.5%, stops early for futility 59.1% of the time, and the average number of randomizations is 426. If the effect is uniform across cells at 0.32 (scenario #1), the fixed-sample design is optimal, but the adaptive design results in only a small loss of power (from 95.8% to 86.0%), but reduced the expected sample size (from 560 to 376). We observed similar findings when the effect is uniform across cells at 0.3 (scenario #2). The adaptive design performs much better (higher power and smaller expected sample size) than the fixed-sample design when the effect size distribution across the subgroups is in accord with the biological assumptions (scenarios #3, #4 and #5). If the effect is concentrated only in Group 1 (scenario #6) or Group 1A (scenario #7), the adaptive design maintains power (70.6% in scenario #6 and 60.5% in scenario #7) while the conventional design collapses (21.2% power in scenario #6 and 12.8% in scenario #7).

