Under our design setting (maximum sample size $N=560$ and conducting interim analysis at $N=200$ and $N=380$ with type I error at 0.025 and power at 0.9), we obtain $b = 2.604$, $\tilde{b} = -1.897$, $c = 2.772$ for our efficacy and futility boundaries. We assume θ to be the projected treatment effect given the maximum sample size for testing the hypothesis: $H_0: P(Y \leq X) = \frac{1}{2}$, $H_A = P(Y \leq X) = \frac{1}{2} + \theta$ using the fixed-sample-size test and is calculated as $\frac{(Z_{1-\alpha} + Z_{1-\beta})}{\sqrt{3N}} = 0.0791$. Here, Y denotes the Rankin score in the medical management group and X denotes the Rankin score in the endovascular group. The rationale of this set-up is detailed in section 3.1 of Lai et al (2014).

Reference

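### The final analysis turns a missed superiority bound into a declaration that EVT has no benefit, with no interval or margin behind it

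*Combined protocol and SAP*

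**What the plan says.** Section 6.1, Final analysis, has two routes.

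- **Scenario (1), enrollment never restricted.** The overall population is tested first. On a miss, "If the efficacy bound is not crossed, the optimal subgroup is selected and the null is tested in that group". If the subgroup test also misses, option 2.2 applies: "If the efficacy bound is not crossed, EVT will be declared of no benefit".
- **Scenario (2), enrollment restricted at an interim.** Only the selected subgroup is tested, and "Efficacy or lack thereof will be declared as per options 2.1 and 2.2 above".

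Appendix B gives the interim efficacy bound b = 2.604, the futility bound -1.897 and the final bound c = 2.772. Section 6.1 sets the futility bound at the interim analyses only. For the primary endpoint, Section 6.1 names a Wilcoxon-Mann-Whitney test and a stratified CMH test, but specifies no effect estimate or confidence interval. Adjusted odds ratios with 95% intervals are promised under Secondary analyses.

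**The concern.** At each interim look the plan recognises three states: efficacy, futility, and neither. At the final look the third state disappears and everything short of efficacy is called no benefit. That label is a claim about the treatment, yet its only support is that a strict superiority bound (one-sided p = 0.0028) was not reached. Nothing in the rule asks whether the data exclude an effect worth having.

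This would be the trial's main negative conclusion, in a population that Section 1.1 describes as lacking randomized evidence. If the label is attached to data still compatible with the planned effect, readers will take it as evidence against thrombectomy.

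**Working it through.** **Inputs.** From Section 6.1: projected 90-day mRS of 4/8/12/16/19/13/28% (EVT) and 1/4/9/14/19/10/43% (medical management), standardized effect 0.34, fixed N of 376, looks at 200, 380 and 560, and group shares of 14/6/14/6/42/18%. From Appendix B: b, c, the futility bound and theta = 0.0791. From Section 3.4: allocation 1:1.

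**1. Reproduce the plan's figures.** P = P(EVT better) + 0.5 P(tie) = 0.0398 + 0.0776 + 0.1086 + 0.1264 + 0.11875 + 0.0624 + 0.0602 = 0.59375. With tie factor 0.9421, N = 4(1.960 + 1.282)² × (0.9421/12) / 0.09375² = 375.4, so 376, as stated. Theta = (1.960 + 1.282)/√(3 × 560) = 0.0791, as stated.

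**2. Which final overall Z values are compatible with the planned effect?** At 280 per arm without ties, SE(P) = 1/√1680 = 0.0244. The upper nominal 95% limit reaches P = 0.59375 when Z = 0.09375 × √1680 - 1.96 = 3.84 - 1.96 = 1.88. On the standardized scale, with Wilcoxon efficiency 3/π, the divisor is √(140 × 3/π) = 11.56, and the limit reaches 0.34 at Z = 0.34 × 11.56 - 1.96 = 1.97. The threshold is therefore about 1.9 to 2.0.

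| Overall Z | Effect | Nominal 95% interval | Interval with multiplier 2.772 |
|---|---|---|---|
| 1.96 | 0.17 | 0.00 to 0.34 | -0.07 to 0.41 |
| 2.77 | 0.24 | 0.07 to 0.41 | 0.00 to 0.48 |

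With the 2.772 multiplier, a rough allowance for the design, both intervals contain the planned effect and also reach zero (just, at 2.77). The data in this range are inconclusive.

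**3. How often does the label fall on a trial with a real effect?** The design was simulated with 40,000 trials per scenario, using the bounds, looks and group shares above. Two assumptions were needed: c also applies to the final subgroup test, and theta is recomputed for the reduced maximum N after selection.

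| Uniform effect | Power: simulated (stated) | Final no-benefit label | Of which overall Z 1.96 to 2.77 |
|---|---|---|---|
| 0.34 | 91.7% (about 91%) | 8.1% | 6.0 points |
| 0.32 | 87.8% (86.0%) | 11.8% | 8.2 points |
| 0.30 | 82.8% (81.1%) | 16.5% | 10.8 points |

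The stated power caps the first row: 100 - 91 leaves about 9% of trials at 0.34 without an efficacy claim, early futility stops included.

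**4. How often does the subgroup test rescue a near miss?** Among trials with a final overall Z of 1.96 to 2.77, the share ending with the label is 6.0/7.3 = 82% at uniform 0.34, 4.8/21.4 = 22% in Table 3 scenario #3 and 1.3/12.5 = 10% in scenario #4.

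**5. Where the simulation does not match.** Under the null it gives 46% early futility stops and an average of 457 patients, against the stated 59.1% and 426. The stated figures allow at most 100 - 59.1 - 2.0 = 38.9% final no-benefit declarations under the null; the simulation gives 51.9%. The relaxed futility rule after selection is not given in enough detail to reproduce. Type I error agrees (2.1% against 2.0%).

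**The case against.** The strongest defence is that the phrase is only the failure branch of a testing algorithm, restated in the next paragraph as efficacy or its lack, and that no bound, alpha, power or sample size depends on it. That is true and limits the weight of the point. It does not remove it: this is a prespecified declaration, and no primary-effect interval is planned that would correct the reading.

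Several stronger readings are tempting, and the documents do not support them.

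- *An overall Z of 2.7 would be reported as no benefit.* Only if the selected subgroup then also fails. Under heterogeneous effects it usually does not fail (step 4).
- *Efficacy should be claimable from 1.96.* No. The bound of 2.772 is the price of the interim looks and subgroup selection, and withholding the claim below it is correct.
- *By the plan's own futility statistic, any Z above 1.345 leaves the planned effect open.* That limit is 0.0791 × √1680 - 1.897 = 3.242 - 1.897. It uses theta = 0.0791, a standardized effect of about 0.28. The planned effect is P = 0.594, which the nominal interval excludes for Z below about 1.88.
- *Table 3's shortfalls in power (14% to 39.5%) count as false declarations.* They are type II error, disclosed in the plan, include early futility stops, and would be the same under any wording.

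It is also fair to object that applying c to the final subgroup test is an inference: Appendix B states c for the whole population and b for the selected subgroup. Using b instead lowers the final no-benefit share from 24% to 19% in scenario #3 and from 30% to 25% in scenario #5. Using c fits Table 3 better.

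**Conclusion.** The point holds as a defect in the prespecified conclusion. Option 2.2, and its use in scenario (2), asserts no benefit on the strength of non-rejection alone, in the last population tested. An overall Z of about 1.9 to 2.77 at N = 560 is compatible with the planned effect by a nominal interval and can still be given this label when the subgroup test also fails. At a uniform 0.34 effect this ending occurs in about 8% of trials, about 6 points of it with overall Z above 1.96.

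Those shares rest on the two simulation assumptions and on a futility rule that could not be matched. An easier futility stop, or b in place of c for the subgroup, would lower them. The logical fault depends on none of this. It is not an error in alpha, power or sample size.

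**What to change.** 1. Reword option 2.2, and its application in scenario (2), to say that efficacy was not demonstrated.
2. Report P(EVT better) + 0.5 P(tie) for the overall population and for any selected subgroup, with a confidence interval that accounts for the interim looks and the selection. Name the interval method in advance.
3. Conclude absence of a worthwhile benefit only if that interval excludes the planned effect. Otherwise call the result inconclusive.

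The Appendix B futility statistic should not serve as this criterion. Its bound is set for interim looks and relaxed after selection. In a small subgroup such as G1A (14% of 560, about 78 patients) it would need Z at or below 0.0791 × √(3 × 78) - 1.897, about -0.7, so the data would have to favour control.

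The cost is SAP wording and one interval method. No patients or alpha are spent, and the bounds and power stay as they are. The small downside is that some negative trials will be reported as inconclusive.
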